## 2.4 Rationale

[figure not shown]
The effect of blinatumomab in the treatment of NHL was tested in a dose escalation study (Study MT103-104 [Goebeler et al, 2016]). A dose dependent clinical response was observed and objective clinical responses were seen starting at 15  $\mu\text{g}/\text{m}^2/\text{d}$  (~28  $\mu\text{g}/\text{day}$ ) and peaked at 60  $\mu\text{g}/\text{m}^2/\text{d}$  (~112  $\mu\text{g}/\text{day}$ ). Due to transient cytokine release after initiation of treatment, a step-dosing regimen was implemented to minimize cytokine related adverse events. An effective step-dose regimen of 9  $\mu\text{g}/\text{d}$  (week 1)-28  $\mu\text{g}/\text{d}$  (week 2)-112  $\mu\text{g}/\text{d}$  (remaining weeks) following cIV infusion for 8 weeks was established for the treatment of diffuse large B-cell lymphoma in study MT103-208 (Viardot et al, 2016). In this study, the blinatumomab concentration levels following the cIV regimen will be used as a reference to guide dose selection of SC administration. The target SC dose for the treatment of NHL is a dose that can achieve a similar exposure (area under the curve) as that of 112  $\mu\text{g}/\text{d}$  dose under cIV. To facilitate the SC dose selection, PK simulation was performed with the PK parameters (clearance and volume of distribution) generated from human studies under cIV and an assumed bioavailability of 0.25 in humans which was an approximate average of bioavailability in mouse (0.35), rat (0.16), monkey (0.21) and pig (0.30) under SC administration.

The simulated PK profiles of cIV (9/28/112  $\mu\text{g}/\text{d}$ ) and SC every day (112/450) and twice a day ([BID] 56/225  $\mu\text{g}/\text{dose}$ ) are provided in Figure 3. Based on currently available information on bioavailability and exposure, 450 (or 225  $\mu\text{g}/\text{BID}$ ) is the estimated SC equivalent dose to the cIV 112  $\mu\text{g}/\text{d}$  dose.

The assumption will be examined in Period 1 of this study following the PK assessment in the cIV run-in phase and then SC administration.

The calculated bioavailability for SC administration, the PK profiles of SC as well as safety and tolerability data will be used to assess the doses recommended for the Period 2 of the study.

**Figure 3. Simulated Blinatumomab Concentration-time Profiles Under Continuous IV Infusion and Under Once (1a) or Twice (1b) Daily Subcutaneous Administrations**

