## 3. EXPERIMENTAL PLAN

### 3.1 Study Design

The overall study design is described by study schemas in Figure 1 and Figure 2 at the end of the protocol synopsis section.

This is a global multi-center, Phase 1b open-label study investigating the safety and PK of blinatumomab administered subcutaneously for the treatment of relapsed/refractory indolent NHL. The SC administration of blinatumomab will be tested for the first time in humans.

Approximately **30** subjects' evaluable for dose limiting toxicities (DLT) will be enrolled in Period 1 (6 evaluable subjects in each dose-cohort). The focus of this period is to determine the PK, bioavailability, and safety profile of blinatumomab SC administration. The PK and bioavailability data from Period 1 of the study will be used in conjunction with safety data (DLT) to determine the SC MTD. The MTD or the maximum tested dose, if MTD is not reached, will be further tested in Period 2 in an expanded cohort of up to 15 additional **evaluable** subjects. Efficacy of blinatumomab administered subcutaneously will also be investigated in each period of the study.

### 3.1.1 Cycle 1/Period 1

In Period 1, **3 or more** separate dose cohorts of up to 6 DLT evaluable subjects each will be enrolled. Subjects will undergo an initial cIV blinatumomab run-in period (weeks 1 to 3) followed by **a 12-hour treatment free period, and then receive** SC administration (week 4). After **a treatment free period of 2 to not more than 3 days**, subjects receive cIV treatment to complete 6 weeks of therapy (weeks 5 to 6) **Figure 1**.

For all cohorts, the initial cIV dose of blinatumomab will be 9 µg/day for the first 7 days (to mitigate for potential cytokine release syndrome [CRS] and neurologic events associated with introduction to blinatumomab) which then will be escalated (dose-step) to 28 µg/day starting on day 8 through day 14 (week 2), and to 112 µg/day starting on day 15 until day 21 (week 3).

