- k **Creatinine clearance to be calculated by Cockcroft-Gault equation.**
- l Lymphocyte subsets for the study are listed above in SOA and are to be collected prior to administration of IP on days 1 and 22, however, additional samples will be collected for adverse events of CTCAE  $\geq$  grade 3 neuro toxicity and CRS occurs throughout the study at the start and resolution of the event (**refer to Section 7.3.16.1**).
- m Disease assessments are to be performed to establish staging and response per Cheson **if disease assessment is by CT scans (Appendix A)** and Lugano criteria **if disease assessment includes PET/CT (Appendix B)**. For PET-CT, CT, or contrast enhanced CT the same imaging modality should be used throughout the study for an individual subject. Disease assessment to occur: during screening; just prior to optional cycle 2 if given (attempt to obtain this study at least 2 weeks after stopping IP in cycle 1 and just prior to starting cycle 2); and the last disease assessment is 4 weeks after finishing the last dose of IP. If PET and CT are acquired on the same day, it is strongly recommended that PET is performed prior to the CT with IV contrast.
- n Bone marrow biopsy to be performed according to Cheson ([Appendix A](#)) and Lugano criteria ([Appendix B](#) [standard of care per investigator]).
- o Bone marrow biopsy performed within 21 days of the first dose of IP may be used in place of screening assessment to establish staging or response per Cheson ([Appendix A](#)) and Lugano criteria ([Appendix B](#)).
- p Anti-blinatumomab antibody predose on day 1, before the administration of first SC dose (following 12 hour wash out from cIV), and predose at the re-start of cIV infusion (following the 2 to 3 day washout).
- q **Cytokine sample on days 1 and 22: predose and at the following time points postdose, 2 hours ( $\pm$  15 minutes), 4 hours, 6 hours ( $\pm$  30 minutes for both the 4 and 6 hour time points), and 12 hours (before the next injection in case of q12h dosing  $\pm$  1 hour). Additional samples will be collected for adverse events of CTCAE  $\geq$  grade 3 neuro toxicity and CRS occurs throughout the study at the start and resolution of the event (Refer to [Section 7.3.16.2](#)).**

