10.8 Pharmacodynamic Analysis

Time profiles of pharmacodynamic markers (eg, T-cell, B-cell, cytokines) may be provided if data are sufficient. Mean (SD) peak (eg, cytokine) or trough concentrations (eg, B-cells) of pharmacodynamic markers will be summarized with descriptive statistics by dose level, cohort and route of administration. Time to reach peak or trough concentrations of pharmacodynamic markers may be summarized by dose, cohort and route of administration.

11. Changes From Protocol-specified Analyses

There are no changes to the protocol-specified analyses.

12. Literature Citations / References

13. Prioritization of Analyses

There is no prioritization of analyses.

14. Data Not Covered by This Plan

Exploratory data not included in this plan may be analyzed at a later date or may be analyzed by a different Amgen Department.

15. Appendices

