Appendix F. DLRT Output List

Following analyses will be done by Biostatistical Science group and the output will be sent to Clinical Study Manager by a pre-defined timeline. In addition to the following list PK data is essential for the DLRT decision making which will be provided from PK group. Also, if available Antibody, Cytokine and Lymphocyte subset data will also be presented in DLRT.

Listings:

For each cohort, following data listings will be provided in an Excel spreadsheet where each listing will be included in a separate worksheet.

1. Subject demographics
2. Date, time, dose of investigational product administration
3. Vital signs
4. Reported adverse events (AEs)
5. Safety laboratory data (Chemistry, Hematology, Urinalysis, Coagulation)
6. Medical history
7. Concomitant medications
8. Prior therapy data

Figures:

Following line plots will be presented for each individual subject:

1. Line plot of vital signs by time course
2. Line plot of all safety labs (Chemistry, Hematology, Urinalysis) by time course

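### In Period 1, the planned summary of peak cytokines by route cannot be read as a route effect: scheduled cIV values are all first-exposure, and scheduled SC values all follow three weeks of cIV

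*Protocol*

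**What the plan says.** **Sampling.** Protocol Table 3, footnote q, reads: "Cytokine sample on days 1 and 22: predose and at the following time points postdose". The post-dose times are 2, 4, 6 and 12 h. Nothing is scheduled at the day 8 or day 15 dose steps, or at the return to cIV on day 29. Footnote q also calls for samples at the start and resolution of grade 3 or higher neurotoxicity or CRS.

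**What the two days are.** Under Protocol 3.1, "the initial cIV dose of blinatumomab will be 9 µg/day for the first 7 days", so day 1 is the first exposure to the drug. As for day 22, "Subjects will undergo an initial cIV blinatumomab run-in period (weeks 1 to 3) followed by" a 12-hour gap and then SC dosing. By that point subjects have had 9, 28 and 112 µg/day for a week each.

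**Analysis.** SAP 10.8 says that mean (SD) peaks of pharmacodynamic markers "will be summarized with descriptive statistics by dose level, cohort and route of administration". Time to peak is optional. SAP section 6 sets baseline for every endpoint at day 1 of the first cycle. SAP 10.6.2 allows plots of biomarker change from baseline.

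**Period 2.** Subjects start directly on SC, at the estimated equivalent of 9 µg/day cIV. Protocol Table 6 shows cytokines at 6 h and 24 h after that first dose.

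**The concern.** The protocol itself ties cytokine release to the start of treatment (Protocol 2.4): "Due to transient cytokine release after initiation of treatment, a step-dosing regimen was implemented to minimize cytokine related adverse events". A first-exposure sample and a sample taken after three weeks of treatment are then different measurements, whatever the route. In Period 1 the first kind is always cIV and the second always SC. A reader given peak cytokines split by route will naturally take a gap between the columns as a property of the route. The SAP does not warn against this.

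The baseline rule adds a second problem. If day 22 changes are measured from day 1, they contain whatever the cIV run-in did to the cytokine level as well as the response to the SC dose. A predose sample is taken on day 22 and would avoid this.

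**Working it through.** The documents give no sample size, power or precision figure for cytokines, so there is no planned figure to reproduce. The check is whether route can be separated from the other differences.

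**1. Scheduled first-dose cells**

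| Occasion | Route | Prior exposure | Dose | Post-dose times |
|---|---|---|---|---|
| Period 1 day 1 | cIV | none | 9 µg/day | 2, 4, 6, 12 h |
| Period 1 day 22 | SC | 3 weeks cIV to 112 µg/day | cohort SC dose | 2, 4, 6, 12 h |
| Period 2 day 1 | SC | none | SC equivalent of 9 µg/day | 6, 24 h |

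Sources: Protocol Table 3 footnote q, sections 3.1.1 and 6.2.1.1.2, and Table 6.

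**2. Route against prior exposure.** Use three terms: intercept, SC route (0/1), prior exposure (0/1).

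- Period 1 alone has rows (1,0,0) and (1,1,1). The rank is 2 of 3. The day 22 minus day 1 difference estimates route + prior exposure, and the two cannot be split. This holds for all of the roughly 30 Period 1 subjects, because no scheduled sample is cIV after exposure or SC without it.
- Adding Period 2 day 1, row (1,1,0), gives rank 3 of 3. Route becomes estimable, but only between different subjects and only if there is no period or cohort effect.

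**3. Dose.** Ratio = SC daily dose × F ÷ 9 µg/day. Protocol 2.4 assumes F = 0.25, with animal values from 0.16 to 0.35. SC daily doses are 2 × 112 = 224 µg (cohort 1) and 2 × 225 = 450 µg, or 450 µg once daily (cohorts 2 and 3).

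| F | 224 µg/day | 450 µg/day |
|---|---|---|
| 0.16 | 35.8 ÷ 9 = 4.0 | 72.0 ÷ 9 = 8.0 |
| 0.25 | 56.0 ÷ 9 = 6.2 | 112.5 ÷ 9 = 12.5 |
| 0.35 | 78.4 ÷ 9 = 8.7 | 157.5 ÷ 9 = 17.5 |

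These are daily-rate ratios, not ratios of peak concentration. They show that the day 22 systemic dose is several times the day 1 dose under any of the three values of F.

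**4. Baseline.** For a day 22 post-dose value:

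(day 22 post − day 1 predose) = (day 22 post − day 22 predose) + (day 22 predose − day 1 predose).

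The first term is the change after the SC dose. The second is the net effect of the run-in and the 12-hour gap. The day 1 baseline reports the sum.

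**5. Shared times for a first-exposure contrast.** {2, 4, 6, 12} and {6, 24} have only 6 h in common. A maximum over 2 to 12 h and a maximum over 6 and 24 h are not the same quantity. Table 6 defines an abbreviation for baseline that does not appear in the text available here, so a Period 2 predose sample may exist. It would not add a shared post-dose time.

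**The case against.** **No route comparison is claimed.** The exploratory objective concerns cytokine profiles during SC dosing, no hypothesis is tested, and SAP 10.8 is descriptive. This stands, and it limits the weight of the point. It does not remove it, because a table with route as a heading invites the comparison.

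**The summary is already split by dose level and cohort.** Also true. In Period 1 the 9 µg/day cIV cell is day 1 and the SC cells are day 22, so labelling by occasion largely renames the same cells. The gain lies in the label, the stated limit and the same-day predose reference.

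**The data are wider than two days.** Event-triggered samples exist, but they are selected by the outcome and cannot repair the contrast. SAP 10.8 also covers Period 2, which supplies first-exposure SC values. It would therefore be wrong to say that the study holds no information on route; the limit applies to Period 1.

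**SC peaks must come out lower.** A reader might infer this from the prior exposure. The documents do not support it. They contain no cytokine data, the higher SC dose could push the other way, and Protocol 6.2.1.3 treats each dose step, not just first exposure, as a CRS risk. The net direction is unknown.

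**The DLRT would be falsely reassured about Period 2.** A reader might infer this too, since Protocol 6.2.1.2.1 includes PK/PD information in the DLRT review. But Protocol 3.1.2 bases Period 2 doses on PK, bioavailability, safety and DLRT review. SAP Appendix F says that "if available Antibody, Cytokine and Lymphocyte subset data will also be presented in DLRT", and the outputs it specifies are cohort listings and individual line plots, not the by-route table of SAP 10.8. Period 2 also has its own dose steps, monitoring, cytokine samples and DLT stopping rule. The harm is not shown.

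**Conclusion.** The point holds for the scheduled Period 1 cytokine data. Route is completely aliased with prior exposure (rank 2 of 3), and the SC daily dose reaching the circulation is about 6.2 to 12.5 times the day 1 cIV dose at F = 0.25, or 4.0 to 17.5 times over the animal range. A Period 1 difference between routes is uninterpretable in either direction. Separately, the day 1 baseline would mix the run-in effect into any day 22 SC change that is presented.

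The aliasing follows from the sampling schedule and needs no assumption. The dose ratios rest on the assumed bioavailability and cover cohorts 1 to 3 only. The endpoint is exploratory and descriptive, and no primary or secondary result depends on it. The change is still worth making, because it costs nothing and uses samples already planned.

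**What to change.** **In SAP 10.8 (wording only, no new data):**

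- Present Period 1 cytokines by occasion: day 1, first cIV exposure; day 22, SC after the cIV run-in.
- Take changes from the predose sample of the same day, as a stated exception to the section 6 baseline.
- State that the two occasions do not form a route comparison.
- If route is of interest, describe Period 1 day 1 (cIV) beside Period 2 day 1 (SC, 9 µg/day equivalent) at 6 h. Say that the subjects are different and were enrolled sequentially, and that peaks are not like for like because the sampling times differ.

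The cost is a few sentences and one small table.

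**Optional, by protocol amendment:** add a 24 h cytokine tube on days 2 and 23, when Table 3 already has hematology and chemistry draws. For the first-exposure description, the day 2 tube would make 24 h a second shared time. The cost is two tubes per subject, and only subjects not yet treated would contribute.

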**Table 4. Cycle 1/Period 1 Investigational Product Dosing and PK Assessments for Week 4 and 5**

Study Part	Subcutaneous Administration (Doses tested sequentially in separate cohorts)							cIV to complete 6 weeks of treatment			
	22	23	24	25	26	27	28	29	30	31	37
Cycle Day											
Cycle Week	4							5			6
q12h											
Blinatumomab	X b	X b	X b	X b	X b	X b		X	X	X	X
Blinatumomab PK sample a	X c				X c	X c	X c		X d		
q24h											
Blinatumomab	X b	X b	X b	X b	X b	X b		X	X	X	X
Blinatumomab PK sample a	X c				X c	X c	X c		X d		
q48h											
Blinatumomab	X b		X b		X b			X	X	X	X
Blinatumomab PK sample a	X c				X c	X c	X c		X d		
q72h											
Blinatumomab	X b			X b				X	X	X	X
Blinatumomab PK sample a	X e			X e	X e	X e	X e		X d		
q96h											
Blinatumomab	X b				X b			X	X	X	X
Blinatumomab PK sample a	X c				X c	X c	X c		X d		
q7d											
Blinatumomab	X b							X	X	X	X
Blinatumomab PK sample a	X f	X f	X f	X f	X f				X d		

Abbreviations: cIV = continuous intravenous; CRS = cytokine release syndrome; CTCAE = Common Terminology Criteria for Adverse Events; PK = pharmacokinetic; q12h = every 12 hours; q24h = every 24 hours; q48h = every 48 hours; q72h = every 72 hours; q96h = every 96 hours; q7d = every 7 days; SC = subcutaneous

a Additional PK samples will be collected for adverse events of CTCAE ≥ grade 3 neuro toxicity and CRS occur throughout the study at the start, 24 hours after the event and at the resolution of the event. PK data will be collected for CTCAE ≥ grade 3 adverse events of CRS or neurotoxicity that occurs during SC administration. Obtain the samples as close as possible to the start of the event, at approximately 24 hours after the event and at the end of the event when all symptoms are resolved. Refer to [Section 7.3.15.1](#).

b If a subject has a dose interruption during the SC administration period and that dose needed to be provided on a weekend, then the dose will be held and dosing will resume on the next business day if the site is unable to administer SC dosing on weekends due to local feasibility challenges. In that case, despite any extra days added due to treatment interruption in the cIV portion, day 22 still refers to the first day of SC administration.

c During SC dosing, at q12h, q24h, q48h, and q96h, PK samples are collected for the first dose on day 22 (pre-dose, as well as 1 hour ± 15 minutes, 2 hours ± 15 minutes, 4 hours ± 30 minutes, 6 hours ± 30 minutes, 8 ± 1 hours, and 12 ± 1 hour (before the next q12h dose if applicable) and for the last dose on day 26 (pre-dose, as well as post-dose at 1 hour ± 15 minutes, 2 hours ± 15 minutes, 4 hours ± 30 minutes, 6 hours ± 30 minutes, 8 ± 1 hours, 12 ± 1 hours, as well as 24 ± 2 hours (day 27), and 48 ± 2 hours (day 28).

d In the return to cIV dosing following the 5 treatment days of SC administration, PK samples are collected at any time during the day on the second day (day 30) after resuming 112 µg/day cIV dose (day 29). Refer [Section 7.3.15.1](#) for detail, sampling window and handling if dose interruption occurred.

e For the SC q72h dosing regimen, PK samples are collected for the first dose on day 22 (pre-dose, as well as 1 hour ± 15 minutes, 2 hours ± 15 minutes, 4 hours ± 30 minutes, 6 hours ± 30 minutes, 8 ± 1 hours, and 12 ± 1 hour and for the last dose on day 25 (pre-dose, as well as post-dose at 1 hour ± 15 minutes, 2 hours ± 15 minutes, 4 hours ± 30 minutes, 6 hours ± 30 minutes, 8 ± 1 hours, 12 ± 1 hours, as well as 24 ± 2 hours (day 26), 48 ± 2 hours (day 27), and 72 ± 2 hours (day 28).

f For the SC q7d dosing regimen, PK samples are collected for the dose on day 22 (pre-dose, as well as 1 hour ± 15 minutes, 2 hours ± 15 minutes, 4 hours ± 30 minutes, 6 hours ± 30 minutes, 8 ± 1 hours, and 12 ± 1 hour as well as 24 ± 2 hours (day 23), 48 ± 2 hours (day 24), 72 ± 2 hours (day 25) and 96 ± 2 hours (day 26).

Approved

**Table 5. Schedule of Assessments for Cycle 1/Period 2**

Study Part	Screening	Treatment Period													Safety Follow-up a, b, c EOS (+ 7 days)
		Period 2 Subcutaneous Administration												EOT (± 3 days)	
		1	2	3	8	9	10	15	16	17	22 t	29 t	36 t		
Cycle Day	-14 to -1	1	2	3	8	9	10	15	16	17	22 t	29 t	36 t	42	
Cycle Week		1			2			3			4	5	6		
GENERAL AND SAFETY ASSESSMENTS															
Informed consent	X														
Inclusion/exclusion criteria	X														
Medical history/ current medical condition	X														
Demographics	X														
ECOG Performance Status	X														X
Physical examination (including neurological examination) d	X	X	X	X	X	X	X	X	X	X	X	X	X	X	X
Hospitalization e		see footnote e below													
Vital signs, temperature f	X	X	X	X	X	X	X	X	X	X	X	X	X	X	X
Concomitant medications	X	X	X	X	X	X	X	X	X	X	X	X	X	X	X
Adverse events g		X	X	X	X	X	X	X	X	X	X	X	X	X	X
Serious adverse events g	X	X	X	X	X	X	X	X	X	X	X	X	X	X	X
Disease related events		X	X	X	X	X	X	X	X	X	X	X	X	X	X
LABORATORY ASSESSMENTS															
Serum or urine pregnancy test h	X														
Coagulation i	X														X
Hematology	X	X	X		X	X		X	X		X	X	X	X	X
Chemistry	X	X	X		X	X		X	X		X	X	X	X	X
Urinalysis	X														
Hepatitis serology, HIV	X														

Approved

Footnotes defined on next page of the table

**Table 5. Schedule of Assessments for Cycle 1/Period 2**

Study Part	Screening	Treatment Period												EOT (± 3 days)	Safety Follow-up a, b, c EOS (+ 7 days)
		Period 2 Subcutaneous Administration													
Cycle Day	-14 to -1	1	2	3	8	9	10	15	16	17	22 t	29 t	36 t	42	
Cycle Week		1			2			3			4	5	6		
LABORATORY ASSESSMENTS (continued)															
Anti-blinatumomab antibody		X n						X u			X u	X u	X u		X
IgG	X													X	X
Lumbar puncture j	X														
Creatinine Clearance s	X														
INVESTIGATIONAL PRODUCT DOSING															
Blinatumomab		see Table 6 below													
BIOMARKER ASSESSMENTS															
Cytokines o		see Table 6 below													
Lymphocyte subsets p		see Table 6 below													
PK ASSESSMENTS															
Blinatumomab PK sample q		see Table 6 below													
DISEASE ASSESSMENTS															
PET-CT, CT or contrast enhanced CT k	X														X
Bone marrow biopsy l, m	X														X r

Page 2 of 2

Abbreviations: CT = computed tomography, ECOG = Eastern Cooperative Oncology Group, EOT = end of treatment, EOS = end of study, HIV = human immunodeficiency virus, HSCT = hematopoietic c stem cell transplant, IgG = immunoglobulin G, INR = international normalized ratio, IP = investigational product, PET = positron-emission tomography, PK = pharmacokinetic, PTT = partial thromboplastin time, SC = subcutaneous.

a If a subject discontinues the study the safety follow-up procedures should be conducted immediately.

b All subjects, including subjects who withdraw from the study, should complete a safety follow-up visit 30 (+ 7) days after the last dose of blinatumomab, or before HSCT or any other non-protocol specified anti-tumor therapy, if applicable.

c Safety follow-up (EOS) should only be done following cycle 1 if treatment is ended after the 6 weeks of blinatumomab and no second cycle is planned to be administered. If a second cycle is planned then obtain the EOS after Cycle 2.

d Physical examination will include weight. Screening only: medical and surgical history, and height will **also** be obtained.

Approved

- e Hospitalization in Period 2: For subjects 1-5: day 1 until completion of the second MTD dose PK being finished. Sites where outpatient PK cannot be obtained, for third MTD SC dose, the subject needs to be hospitalized until completion of the third MTD dose PK. Subjects 6-15: are hospitalized on days 1-8 (discharge 8 hours after day 8, 28 µg/day SC dose is administered) and readmitted to the hospital on day 12 (prior to first MTD SC dose) until 8 hours after the second MTD SC dose is administered. Sites where outpatient PK cannot be obtained, for third 28 µg/day equivalent SC dose and third MTD SC dose, the subject needs to be hospitalized until completion of the third MTD dose PK.
- f The investigator should monitor the subject's vital signs continuously every 4 hours (± 2 hours) during the first 12 hours after the start of each new treatment/dose-step. Subject must be in a supine position in a rested and calm state for at least 5 minutes before blood pressure assessments are conducted. If the subject is unable to be in the supine position, the subject should be in most recumbent position possible. The position selected for a subject should be the same throughout the study. Vital sign measurements will be repeated daily during the subject's hospitalization.
- g Serious adverse events are collected from the time of signing informed consent form to the end of study and adverse events are collected after the first dose of IP.
- h Serum or urine pregnancy test will be performed for all women subjects unless surgically sterile or > 2 years postmenopausal. Additional pregnancy testing may be performed at the investigator's discretion or as required per local laws and regulations.
- i Coagulation will include PTT, INR, and fibrinogen.
- j Lumbar puncture is only needed for disease assessment per standard of care per investigator. Lumbar puncture should be obtained for evaluation of seizures that occur during blinatumomab treatment, if clinically stable, and a sample sent for blinatumomab PK.
- k Disease assessments are to be performed as to establish staging and response per Cheson (Appendix A) and Lugano criteria (Appendix B). For PET-CT, CT, or contrast enhanced CT the same imaging modality should be used throughout the study for an individual subject. Disease assessment to occur: during screening; just prior to optional cycle 2 if given (attempt to obtain this study at least 2 weeks after stopping IP in cycle 1 and just prior to starting cycle 2); and the last disease assessment is 4 weeks after finishing the last dose of IP. If PET and CT are acquired on the same day, it is strongly recommended that PET is performed prior to the CT with IV contrast.
- l Bone marrow biopsy to be performed according to Cheson (Appendix A) and Lugano criteria (Appendix B [standard of care per investigator]).
- m Bone marrow assessment performed within 21 days of the first dose of IP may be used in place of screening assessment to establish staging or response per Cheson (Appendix A) and Lugano criteria (Appendix B).
- n Anti-blinatumomab antibody on day 1 predose
- o Cytokines will be obtained as outlined in the dosing option tables (Table 6); additional cytokine samples will also be collected for adverse events of CTCAE ≥ grade 3 of CRS or neurotoxicity if it occurs (Refer to Section 7.3.16.2). Obtain the samples as close as possible to the start of the event and at resolution of the event (Refer to Section 7.3.16.2).
- p Lymphocyte subsets will be collected as outlined in the dosing option tables (Table 6) additional samples will be collected for adverse events of CTCAE ≥ grade 3 neuro toxicity at the start and resolution of the event (Refer to Section 7.3.16.1).
- q The PK samples will be obtained as outlined in the dosing options table (Table 6). (Refer to Section 7.3.15.2 for sampling times, sampling window and handling for dose interruption). PK data will also be collected in the events of CTCAE ≥ grade 3 adverse events of CRS or neurotoxicity that occurs during SC administration. Obtain the samples as close as possible to the start of the event, at approximately 24 hours after the event, and at the end of the event when all symptoms are resolved (refer to Section 7.3.15.2).
- r Bone marrow biopsy only to be repeated with a response assessment (~ 3 weeks after end of treatment as per standard of care) to establish staging or response per Cheson (Appendix A) and Lugano criteria (Appendix B).
- s Creatinine clearance to be calculated by Cockcroft-Gault equation.
- t Assessments/Lab studies for Day 22, Day 29 and Day 36 (weeks 4, 5, and 6) will be obtained on the day of the first MTD dose given SC that week per interval option determined in Cycle 1/Period 1. Week 4 assessments/labs are obtained Day 22 (for 48h dosing), Day 24 (for q72h dosing), Day 24 (for 96h dosing), Day 26 (for q7 day dosing); Week 5 assessments/labs are obtained Day 30 (for 48h dosing), Day 30 (for 72h dosing), Day 32 (for q96h dosing), Day 33 (for q7 day dosing); Week 6 assessments/labs are obtained Day 36 (for q 48h, 72h, 96h), Day 42 (for q7 day dosing). This allows the assessments/labs to be obtained during clinic visit to receive SC blinatumomab.
- u Anti-blinatumomab antibody will be obtained weekly starting week 3. Please obtain this lab on the first date of the week where lab study assessments are obtained. Please obtain weekly (weeks 3, 4, 5, and 6).

Approved

